## Background and Introduction

---

Perinatal depression occurs in 12%–15% of pregnant and postpartum women and is associated with adverse outcomes for mother, baby, and family, including preterm birth, low birth weight, and impaired cognitive development of the child (Ko, Rockhill, Tong, Morrow, & Farr, 2017; Martin, Hamilton, Osterman, Curtin, & Matthews, 2015; Bonari et al., 2004; Deave, Heron, Evans, & Emond, 2008) Early breastfeeding cessation and reduced ability to parent are also well-documented consequences (Bonari et al., 2004). Nonpharmacological therapies, such as cognitive behavioral therapy (CBT) and mindfulness-based practices (MBP), are known to be as effective as antidepressants for mild to moderate depression, and many pregnant and breastfeeding women prefer not to take antidepressants (O'Connor, Rossom, Henninger, Groom, & Burda, 2016; O'Mahen & Flynn, 2008). However, limited access to and availability of mental health professionals are common barriers to services among women living in rural and low-resource communities (Alang, 2015; Bloom, Bullock, & Parsons, 2012). Lack of consideration for cultural and ethnic variation also creates an additional barrier for many women (for example, Hispanic) (O'Mahen & Flynn, 2008; Baker-Ericzen et al., 2012; Goodman, Dimidjian, & Williams, 2013, The Health Resources and Service Administration [HRSA], 2012). Recommendations for universal screening for perinatal depression during pregnancy and postpartum have left many women and their providers searching for solutions to the current scarcity of resources available to women who screen positive. Telehealth is revolutionizing the delivery of healthcare services and is a promising platform for perinatal mental health care (HRSA, 2012). A telehealth approach will reduce barriers to access and can be tailored to deliver effective services regardless of geographic location (HRSA, 2012). Our pilot work demonstrated feasibility and acceptability of a group video conference intervention (VCI) to deliver nonpharmacological services (CBT and MBP) to women experiencing perinatal depressive symptoms (PDS) ([name], Dorn, Ozawa-Kirk, & Allred, in review; [name] et al., in review). Our research team incorporated participant feedback into revising the VCI, including the use of a low-cost, easy-to-access Web-based platform and use of any electronic device (laptop, tablet, smartphone, or landline) to join facilitated VCI groups of six women. To build on our pilot work, we propose to evaluate the effectiveness of the VCI to reduce PDS and anxiety (a highly comorbid condition) by conducting a randomized controlled trial among women experiencing mild to moderate PDS, as measured by the Edinburgh Postnatal Depression Scale (EPDS).

## Purpose and Objectives

---

The study will evaluate the effectiveness of a videoconference intervention (VCI) to reduce perinatal depression symptoms (PDS) and anxiety (a highly co-morbid condition) by conducting a randomized controlled trial among women experiencing mild to moderate PDS, as measured by the Edinburgh Postnatal Depression Scale (EPDS). Furthermore, we propose to evaluate differences in response to the VCI between subgroups of childbearing women; Hispanic and North European Descent populations, and rural and urban-dwelling.

Specific aims of the study include:

Aim 1: Evaluate the effectiveness of a VCI to reduce PDS and anxiety, as measured by EPDS and Generalized Anxiety Disorder-7 Item (GAD-7) scores across pregnancy and the postpartum. Methods: Pregnant women of all gestational age up to 6 months postpartum (n = 240) who screen positive for mild to moderate PDS (EPDS scores 9–20) will be randomly assigned to VCI or AC for eight weeks. Both groups will continue with standard care as directed by their primary/prenatal care providers. The EPDS and GAD-7 will be administered at three time points during pregnancy and at 2, 4, and 6 months postpartum. Hypothesis: Women participating in the VCI will have significantly lower post intervention EPDS and GAD-7 scores across pregnancy and postpartum than women in the AC group.

Secondary Aim 1: Explore differences in the effectiveness of the VCI to reduce PDS and anxiety across women who enroll at different stages of their pregnancy or postpartum periods.

Aim 2: Evaluate the interaction of the VCI with specific subgroups: ethnicity (Hispanic, North European descent), geographic location (rural, urban), and the outcome of PDS as measured by EPDS and GAD-7 scores across pregnancy and postpartum. We will oversample in Hispanic and rural populations to ensure sufficient representation from diverse groups. Hypothesis: Women will demonstrate differences in EPDS and GAD-7 scores across pregnancy and postpartum, dependent on their study group membership.

Secondary Aim 2: Explore an additional subgroup analysis, namely between those who are and who are not taking medication at the time of screening.

## **Study Population**

---

**Age of Participants:** 18+

**Sample Size:**

At Utah: 240

All Centers:

**Inclusion Criteria:**

The study will include women 18 years of age and older who, at time of enrollment (1) have a viable pregnancy or have given birth within the previous 6 months, (2) have an Edinburgh Postnatal Depression Scale (EPDS) score of 9–20; (3) are English- or Spanish-speaking; and (4) are attending a collaborating prenatal or public health clinic associated with the University of Utah or Utah Department of Health.

**Exclusion Criteria:**

The study will exclude women who, at time of enrollment (1) have an EPDS score <9 or >20; (2) have a current diagnosis of a serious mental illness, such as psychosis,

schizophrenia, bipolar disorder, severe depression, or suicidality; or (3) have begun taking or changed dosage of any medication for a mental health condition within the past 6 weeks

## Design

---

Randomized Trial

## Study Procedures

---

### **Recruitment/Participant Identification Process:**

#### VCI/AC Sessions

Each study clinical site has implemented a universal electronic screening for perinatal depression, which ensures that all women receiving services at all study facilities are screened during pregnancy and postpartum. In addition, staff at the collaborating sites inform women about the study by way of flyer or direct interaction. No one is involved in consenting participants or in delivering the interventions. Flyers could be handed out to potential participants or would be available at study sites (e.g., on walls with site's approval). Handing out flyers would help patients think about participating in the study for those who cannot make a decision at the study site. Screening includes the Edinburgh Postnatal Depression Scale (EPDS) and is self-completed by patients at the time of a clinical office visit. Patients complete the screening in the clinic using an electronic device (tablet, computer, or their own Smartphone) as soon as possible when they come in. Screening results are integrated into the Electronic Health Record (EHR) and/or electronic database managed by the University of Utah. Results are immediately available electronically to the patient and her healthcare provider for evaluation, management and/or referral. These electronic screening results are also available to study staff for the purposes of identifying potential study participants, i.e. positive screening results (greater than 9 on EPDS). The electronic screening process conveniently includes an item that allows patients to indicate their interest in receiving additional information and/or agreement to be contacted as a potential research participant. Those who agree will be contacted by study staff by phone or email. Alternatively, a patient can contact the study staff herself. Women who screen positive, are determined eligible to participate by study staff, and are interested in participating are contacted by study staff to discuss the study and complete the informed consent process. Informed consent is completed by telephone or video conference platform. The consent form is sent to potential participants via REDCap email or the U.S. Postal Service, if there is no email address. Eligibility is confirmed through EHR, particularly for confirming gestational age, maternal age, medication status, mental health diagnoses, etc. All potential participants are screened for suicidal and homicidal ideation, and if either are present the individual is immediately referred to a mental health professional for further evaluation, and to determine appropriateness for participating in the study.

Social media (Twitter, Instagram, and Facebook) will also be used to recruit and inform potential participants about the study. Short video clips will be played on clinic monitor screens with information about the study and small study cards will be available to take home if interested in the study. The study staff will also utilize community events to raise awareness of the study.

Radio advertisements will be used to recruit participants for the study. This will specifically be relevant for the Latina population, based on feedback from community partners.

QR code/survey link will be used to recruit participants by allowing them to take the screening on their own and give their contact information if they are interested in learning more about the study.

We will coordinate with members of the data science service at the University of Utah to identify patients who (1) have agreed to be contacted regarding research studies and (2) meet our inclusion criteria. Members of the data science service will share a report with the research team that includes patient information, such as: name, age, sex, ethnicity, pregnancy/postpartum status, email, and mobile phone number. The research team will use this information to send study invitations via email (and printed mail, if needed) to potential participants. These emails will include information for easy-to-follow steps for opting out of the study. Individuals who elect to opt-out of the study will be removed from future communication and their information will be removed from study data. Anonymous demographic data from opt-out individuals may be retained for the purposes of describing the demographics of the total population considered for this study. Individuals who do not elect to opt-out will be contacted again (up to three times) by the research team, either via email, phone call, text, or print mail.

### Focus Groups

Participants for the pre-intervention Latina focus groups will be recruited via word of mouth, community events, social media, video clips in clinics, and recruitment flyers, utilizing study staff's contacts within the Latina community. These same methods will be used to recruit participants for the main study arm.

Participants for the additional focus groups related to perceptions of mental health and recruitment will be recruited through the Community Collaboration & Engagement Team (CCET) at the University of Utah. An informational recruitment flyer will inform potential participants of the opportunity to participate. Note: American Indian populations will not be recruited without proper approval from appropriate groups

### **Informed Consent:**

#### **Description of location(s) where consent will be obtained:**

Telephone or video conference at a time that is convenient to the woman and research team member.

#### **Description of the consent process(es), including the timing of consent:**

Women who screen positive (EPDS score of 9-20) as part of the universal perinatal depression screening program, and also indicate an interest in the study, will be contacted by study personnel by phone or email. Eligible and interested women receive a study flyer and a consent form by regular USPS mail and/or email attachment. The informed consent process is completed by telephone or videoconference at a time that is convenient to the woman and research team member. A copy of the signed consent form is then exchanged by email attachment or USPS mail.

**Procedures:**  
**Recruitment**

We will coordinate with members of the data science service at the University of Utah to identify patients who (1) have agreed to be contacted regarding research studies and (2) meet our inclusion criteria. Members of the data science service will share a report with the research team that includes patient information, such as: name, age, sex, ethnicity, pregnancy/postpartum status, email, and mobile phone number. The research team will use this information to send study invitations via email (and printed mail, if needed) to potential participants. These emails will include information for easy-to-follow steps for opting out of the study. Individuals who elect to opt-out of the study will be removed from future communication and their information will be removed from study data. Anonymous demographic data from opt-out individuals may be retained for the purposes of describing the demographics of the total population considered for this study. Individuals who do not elect to opt-out will be contacted again by the research team (up to three times), either via email, phone call, text, or print mail.

Each study clinical site has implemented a universal electronic screening for perinatal depression, which ensures that all women receiving services at all study facilities are screened during pregnancy and postpartum. In addition, staff at the collaborating sites inform women about the study by way of flyer or direct interaction. No one is involved in consenting participants or in delivering the interventions. Flyers could be handed out to potential participants or would be available at study sites (e.g., on walls with site's approval). Handing out flyers would help patients think about participating in the study for those who cannot make a decision at the study site. Alternatively, a patient can contact the study staff herself.

Social media (Twitter, Instagram, and Facebook) will also be used to recruit and inform potential participants about the study. Short video clips will be played on clinic monitor screens with information about the study and small study cards will be available to take home if interested in the study. The study staff will also utilize community events to raise awareness of the study.

Radio advertisements will be used to recruit participants for the study. This will specifically be relevant for the Latina population, based on feedback from community partners.

**Enrollment**

Women who have indicated an interest in participating in the study will be contacted by a study team member by text, telephone and/or email to discuss the study and complete the

informed consent process. During that time, eligibility is confirmed through EHR (please see the #4b recruitment/participant identification process), particularly for confirming gestational age, maternal age, medication status, mental health diagnoses, etc. All potential participants are screened for suicidal and homicidal ideation, and if either are present the individual is immediately referred to a mental health professional for further evaluation, and to determine appropriateness for participating in the study.

#### Latina Focus Groups

Those enrolled in the pre-intervention focus groups will participate in a 1-hour focus group. Participants will give feedback on how to tailor the intervention and control group content to best serve Latina participants. There will be a total of 2 Latina groups with up to 10 participants per group.

#### Perceptions of Mental Health and Recruitment Focus Groups

Those enrolled will participate in a 2-hour virtual focus group. These women will fill out a short demographic survey online. Participants will give feedback about experiences of participating in research about and treatment of maternal mental health via telehealth. There will be three focus groups with up to 15 participants each, the first focused on rural Hispanic/Latina women, the second focused on the general rural population, and the third on the rural American Indian/Alaska Native population. These women will receive a \$75 gift card to Amazon or a local grocery store electronically or by mail. Note: American Indian populations will not be recruited or enrolled without proper approval from appropriate groups

#### Stratified Randomization Into Study Groups

After consenting to participate, women will be assigned by computer-generated randomization by two different stratifications (Hispanic/NED and Urban/Rural) to one of two study groups: Videoconference intervention (VCI) or Attention Control. Both groups will continue with standard of care as directed by their prenatal care provider. After randomization, the participant will receive study information pertinent to her specific study group, by mailed hard copy and/or emailed electronic document. Enrollment and randomization will continue until the following enrollment goals are met.

#### VCI Participants

A study team member will contact the participant by telephone and/or email to determine which group start date works best for her and to schedule a time for technology testing and instruction.

#### All Participants: Technology Literacy

Prior to the start date of the first VCI or AC session, each participant will meet with study staff for the purpose of (1) assessing the participant's technology literacy, (2) testing the participant's Internet connection and chosen electronic device, and (3) providing instruction and demonstration for connecting to the videoconference platform (Acano). More than one meeting may be required and will include meeting via Acano and troubleshooting directly

with the participant. After this is completed to the satisfaction of the participant and study staff, the next step will be to schedule the participant to meet with the VCI group facilitator via Acano.

#### Individual Participant Acano Meeting with VCI or AC Group Facilitator

Prior to the first VCI or AC group session, participants will be scheduled for a 30-minute Acano or phone meeting with the individual who will be facilitating the participant's assigned group. The purpose of the meeting is for the facilitator to (1) establish a one-on-one connection with the participant prior to the start of the group, (2) repeat the technology check with the participant, and (3) identify any concerns that would disqualify the woman from study participation (e.g., serious mental health conditions, including severe depression or suicidal ideation that may need immediate referral for more intensive therapy and/or pharmacotherapy).

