#### Clinical Screening Records

Screening that is completed in the clinical setting as part of their routine clinical care is immediately communicated to and addressed by clinical providers at the time of the prenatal or postpartum visit. EPDS and GAD-7 measurements completed periodically and

electronically by enrolled participants as part of the study (not as part of their routine clinical care) are evaluated and addressed by study personnel within 24-48 hours of completion. Participants are contacted directly by study personnel for scores >20 on the EPDS, or if the participant indicates thoughts of harm to self. Furthermore, the EPDS and GAD-7 are electronically scored, interpreted, and communicated to the participant immediately. At that same time, participants also receive electronic resources, including crisis and suicide prevention hot line phone numbers, website links, and study personnel contact information.

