#### Participant-Completed Questionnaires

Questionnaires will be completed by participants via a secure, Web-based data management system (REDCap). Women in all study groups will receive an emailed link to the questionnaire. Study questionnaires are to be completed at six time points: T1 = enrollment; T2 = after group session 9; T3 = 2 months post session 9 T4 = 4 months post session 9; T5=6 months post session 9; T6= 8 months post session 9. In addition to participant demographics, questionnaires will include the EPDS as a measure of the primary outcome of interest: depressive symptoms, as well as the GAD-7 as a measure of comorbid anxiety (GAD-7 is a validated survey). To document the standard of care that all participants receive during study participation, the questionnaire at all six-time points also asks participants to report whether they (1) received a diagnosis of depression, anxiety, or other mental health condition; (2) were prescribed or initiated any medication for depression or anxiety; (3) were referred to and/or engaged in mental health services; and/or (4) have engaged in any type of nonpharmacological therapies for depression/anxiety during the study. If a participant does not have an email address, study staff will assist her to establish and access a free email address. All participants will receive instruction on how to access and complete the study questionnaires. The entire questionnaire takes approximately 15 minutes to complete. Participants receive \$20 for each questionnaire completed.

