## **Data Analysis**

We will use multilevel generalized mixed modeling under an intent-to-treat approach to compare the outcome measures of EPDS and GAD-7 between group 1 (VCI) and Group 2 (AC) at six-time points during pregnancy and postpartum. This is an appropriate statistical approach for the described RCT protocol. Sensitivity analysis was conducted with G-Power 3.1. We used RMANOVA with 6 total measures as a conservative power analysis for our mixed-effects model. The sample is powered for the fixed effect of Intervention X Time. For study aim 1: Using RMANOVA with alpha = 0.5, 6 total measures, 0.3 for correlation between repeated measures, and a sample size of 192 total participants gives greater than 90 percent power to detect an effect size of 0.1, which is a net decrease in EPDS and GAD-7 of roughly 1 point decrease per time point, assuming a standard deviation of 5. For study aim 2: For the stratified samples of urban/rural or Hispanic/NED, we have greater than 80 percent power to detect the same Intervention X Time effect size of 0.1.

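### Women can be disqualified after randomization by a facilitator who knows their arm, and the plan does not say they are still followed up under intent-to-treat

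*Combined protocol and SAP*

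**What the plan says.** **Order of events.** *Stratified Randomization Into Study Groups* assigns women once they have consented, and then: "After randomization, the participant will receive study information pertinent to her specific study group". *Individual Participant Acano Meeting with VCI or AC Group Facilitator* comes later. Before the first session, each woman meets the person who will run her assigned group. One of three purposes is to "identify any concerns that would disqualify the woman from study participation". The examples are serious mental health conditions, including severe depression or suicidal ideation, that may need immediate referral.

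**Before randomization.** *Enrollment* deals with suicidal or homicidal ideation differently. The woman is "immediately referred to a mental health professional for further evaluation, and to determine appropriateness for participating in the study".

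**During follow-up.** *Clinical Screening Records* says: "Participants are contacted directly by study personnel for scores >20 on the EPDS, or if the participant indicates thoughts of harm to self". It does not mention removal from the study.

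**Facilitators.** *UPLIFT Manualized Program* requires a credentialed mental health professional for the VCI sessions. No credentials are stated for AC facilitators.

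**Analysis and timing.** The *Data Analysis* text in the procedures plans "multilevel generalized mixed modeling under an intent-to-treat approach", and the section of the same name under *Statistical Methods* repeats the commitment. Neither says who is in the set. *Participant-Completed Questionnaires* times T2-T6 from group session 9; its second appearance, under *Procedures performed for research purposes only*, times them from the end of the intervention. Aim 1 describes assessments by stage of pregnancy and postpartum, but does not define T2-T6. Enrollment runs until 240 is reached, with no word on whether a disqualified woman counts.

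**The concern.** The disqualifying check comes after randomization, is made by someone who knows the arm, and turns on conditions close to what the EPDS measures. If a woman judged unsuitable leaves the study, the women compared at T2-T6 are no longer the women randomized. Intent-to-treat is a rule about analysis, and it cannot supply questionnaires that were never sent.

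Two features make the gap practical. First, the questionnaire schedule hangs on sessions, so the plan states no follow-up date for a woman who never starts. Second, VCI facilitators are mental health professionals while AC facilitators' background is unstated, so concerns could be detected at different rates in the two arms. At stake is a baseline imbalance created after randomization, which the trial could not see unless it records these cases by arm.

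**Working it through.** **The plan's own figure.** Inputs from *Data Analysis*: "a sample size of 192 total participants", six measures, correlation 0.3, effect size f = 0.1. Alpha is printed as 0.5; I assume 0.05. For the within-between interaction, lambda = N x m x f^2 / (1 - r) = 192 x 6 x 0.01 / 0.7 = 16.46, on 5 and (192 - 2) x 5 = 950 degrees of freedom. Power is 0.898, in line with the stated 90%. The same test is used below.

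**Inputs for the illustration.**
- From the plan: SD 5, r = 0.3, and 4 strata x 30 = 120 women per arm.
- Assumed, because the documents give no rates: one arm loses an extra share p of 5% or 10% (6 or 12 of 120 women). Those women lie D = 5 points (one SD) above the arm mean on whatever drives removal.

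**Shift in the retained mean.** Removing a share p that lies D above the arm mean lowers the mean of the rest by kD, where k = p / (1 - p). This gives k = 0.0526 at 5% and 0.1111 at 10%.

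**One time point, women lost.** The gap carries to another time point with correlation 0.3, so the shift is k x 0.3 x 5 = 1.5k, or 0.079 and 0.167 points. The standard error of the arm difference is 5 x sqrt(2/120) = 0.645, so the shifts are 0.12 and 0.26 SE. A two-sided 5% test at one time point becomes 5.2% and 5.8%.

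**Planned Intervention x Time test.** Let d be the T1 shift minus the common T2-T6 shift. The six shifts then have a sum of squares about their mean of (5/6)d^2. So lambda = (120/2) x (5/6)d^2 / (25 x 0.7) = 2.857 d^2, on 5 and (240 - 2) x 5 = 1190 degrees of freedom.

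| Removal follows | T1 data | T1 shift | T2-T6 shift | d (absolute) at 5%, 10% | lambda | Test size |
|---|---|---|---|---|---|---|
| severity at meeting | lost | 1.5k | 1.5k | 0, 0 | 0, 0 | 5.0%, 5.0% |
| T1 severity | kept | 0 | 0 | 0, 0 | 0, 0 | 5.0%, 5.0% |
| severity at meeting | kept | 0 | 1.05k | 0.055, 0.117 | 0.009, 0.039 | 5.0%, 5.2% |
| T1 severity | lost | 5k | 1.5k | 0.184, 0.389 | 0.097, 0.432 | 5.4%, 7.0% |

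In the third row, the mixed model uses T1 to recover part of the shift: 1.5k - 0.3 x 1.5k = 1.05k. In the fourth, the full 5k appears at T1 and d = 5k - 1.5k = 3.5k.

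With equal removals of the same kind in both arms, every shift cancels.

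**The case against.** The strongest reply is that intent-to-treat ordinarily means all randomized women in their assigned arm, so the plan has already answered the question. The model also allows up to six time points, so a woman with T1 alone need not be dropped. That stands for the analysis set: defining it mostly restates the principle. It does not settle whether T2-T6 are still sent. Session 9 of her assigned group could serve as a date for a woman who never attends, but the plan does not say so.

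It is also fair that the facilitator section asks only that concerns be identified, and that its example is about referral. Stopping sessions alone is a possible reading. Because the words refer to study participation, the text needs reconciling either way.

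A reader might infer more than the documents support:
- **That the treatment effect will be materially biased, or biased toward VCI.** No removal rate is given, so neither size nor direction can be fixed. Eligibility limits, EHR checks and ideation screening all come first, so few cases are likely.
- **That detection does differ by arm.** The unequal statement of credentials makes this plausible, no more.
- **That 5.8% caps the error rate.** It belongs to a single-time-point test; the powered interaction test ranges from 5.0% to 7.0% in the same 10% case.
- **That the gap of 240 - 192 = 48 women was set aside for these removals.** No section says what it covers.

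**Conclusion.** The point holds in a limited form. The order of events is explicit, and a literal reading of the facilitator section conflicts with intent-to-treat. The lasting gap is in data collection: nothing says that a woman found unsuitable at the meeting continues follow-up, or on what dates.

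The effect is unknown and probably small. Under the assumed 5-10% excess removal, D = 5 and r = 0.3, losing the women shifts one time point by about 0.08-0.17 points, against a planned effect of roughly 1 point per time point. The size of the interaction test is 5.0-5.4% at 5% excess and 5.0-7.0% at 10%. A 10% excess in one arm has no support in the documents and serves only as an outer illustration. The case for changing the text rests on its low cost and on data that cannot be collected afterwards. It should be fixed.

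**What to change.** Leave the meeting, the referral and any decision about attending sessions as they are. Reconcile the facilitator section with the two *Data Analysis* sections by adding:

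- Concerns found at this meeting do not end study follow-up. Every randomized woman is analysed in her assigned arm, keeps her T1 data and is sent T2-T6 unless she withdraws consent.
- For a woman who attends no session, T2-T6 dates are set from the planned session dates of her assigned group.
- She counts toward the 240 and is not replaced.
- The monitoring in *Clinical Screening Records* applies to her questionnaires.
- Counts and reasons for concerns raised at the meeting are reported by arm.

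**Cost.** A few sentences, up to five questionnaires at 20 dollars (5 x 20 = 100 dollars per affected woman) and a little more follow-up work. The effect estimate is slightly diluted, because some women in the analysis will not have attended sessions.

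**Editorial only.** *All Participants: Technology Literacy* says "the next step will be to schedule the participant to meet with the VCI group facilitator via Acano", while the next section covers facilitators of both arms. The wording should be aligned.
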